#### Recruitment

After ethical approval of the study protocol in all participating countries, healthcare organizations collaborating with the consortium will provide access to eligible study participants. Principal respectively co-investigators will raise awareness and interest about USECARE AAL in collaborating healthcare organizations based on a study manual (including a refusal list), where clinicians (e.g. physicians and/or designated study nurses) will look-out for eligible participants. Written information material will be provided to inform eligible participants about the study during their regular visits at the respective healthcare organization. Clinicians will provide both oral and written information about the study (see annex 8) and the inclusion and exclusion criteria will be explained to the potential participants. If both the community-dwelling older adult and her/his designated informal caregiver are eligible and agree to participate, their contact data will be forwarded to national investigators of the USECARE consortium to provide additional information about the purpose of the trial, their rights, and possible benefits as well as risks of participation. They will also mail the informed consent sheet for formal willingness to participate (see annex 9) along with the baseline survey questionnaire (including items on socio-demographics, technology acceptance, and medical history).

#### 2.2.3 Intervention

The enhanced SENACA prototype builds on a web platform originally developed for active health promotion and chronic disease risk prevention of older community-dwelling adults (www.senaca.ch). It has been enhanced by its developer to a *cloud-based structured self-management support system with tele-monitoring components* designed to be universally-interoperable with different medical devices, applications and web-based assessment instruments (see Figure 2). The enhanced SENACA prototype can be considered a complex intervention as it contains several interacting components and aims at a variability of behaviours of its users with a range of possible outcomes (Craig et al., 2008).

The enhanced SENACA prototype enables end-to-end wireless connectivity and allows endusers to access biometric data via mobile devices (tablets, smart phones) and personal computers by their choice. The enhanced SENACA prototype combines monitoring and behaviour change elements (under development) with access to evidence-based health information to address two end-user groups: older community-dwelling adults living with chronic conditions (primary end-users) and their designated informal caregivers (secondary end-users). The gathered health data is combined with an a priori individual online risk assessment as part of a personalised health plan and personal health record. The initial assessment allows personalising the intervention to individual end-users using pre-defined algorithms based on international classifications and guidelines. Furthermore, the enhanced SENACA prototype will include motivational behaviour-change and social interaction elements for motivational support.

SENACA aims at "blended" behaviour change and intrinsic motivation with constant feedback. The user will get personalized weekly online feedback on performed tasks (activity, nutrition, health literacy). The language of the formal care goals and suggested protocols will deal with common denominators and final common pathways of most chronic diseases including the three of the study (such as functioning, mood and depression, confusion, falls, abuse and social isolation). In this way USECARE and formal care will best interface, goals will be shared and conflicts avoided. This methodology will enable the enhanced prototype system to take most weight and importance with the three chronic conditions but keep responsibility with the patient in general regarding the formal care.

A behaviour economics (BE) intervention on activity to be tested has already been designed (addressing both informal caregivers and patients), a secondary one is planned on nutrition.

#### Figure 2. Set-up enhanced SENACA prototype

The following are the core components and features of the enhanced SENACA prototype:

**I) a website** (with secured login) and a complementary smartphone application, both for older community-dwelling adults and informal caregivers, which is at the centre of the structured self-management programme that includes five main elements:

1) *personal program* that can be accessed during the trial with personal computers, notebooks or mobile devices owned by end-users

- Personal goals / overview: the end-user's goals pre-defined with consent of the responsible physician focussing on different health indicators, amongst others weight and blood pressure. These goals are targeted within 50 days and should improve until the end of the study period.
- Health data: measured either daily or weekly by monitoring devices (see II)
- *Medication adherence*: full list of all prescriptions with three times a weekly documentation of intake by end-users
- *Nutrition*: an online dietary assessment developed and validated in cooperation with leading Swiss experts (Institute of Epidemiology, Biostatistics and Prevention EBPI, University of Zurich; Institute for Cardiovascular Rehabilitation, Inselspital Bern)
- Physical activity: personalised advice for endurance (same as above) and strength based on the primary end-user's physical constitution assessed by physician. A special program will be modified for the challenged after elective hip/knee replacement with

specific personalized program for the particular person according to his or her condition.

- *Health-related evidence-based knowledge*: an overview of modules and chapters of the SENACA knowledge platform

2) *personal logbook*, where tasks mentioned in the program are confirmed by the end-users on a daily basis. Health data and some activities are automatically collected via the wireless mobile devices. Medication- and nutrition-related activities (i.e. intake of medicines, calories per meal) have to be confirmed manually by the end-users. Unattended tasks are indicated.

3) *personal statistics*, which is a descriptive statistics section of already collected health data including its constantly updated visualisation

4) *personal health record*, which includes personal data from end-users

5) knowledge base including evidence-based information adapted in plain language on hypertension, chronic heart failure, type 2 diabetes and chronic obstructive pulmonary disease (on causes, signs and symptoms, diagnosis, prevention and treatment).

**II) home-monitoring devices** collecting health data of the participants. These will be transferred using Bluetooth technology to a "data aggregator" for encryption and transmission to a dedicated high security server. In the trial, the following devices will be used:

MyGlucoHealth

-	Blood pressure, heart rate	OMRON 708-BT
-	Weight, body fat	OMRON 206-BT
-	Physical Activity	Striive fusion
-	Sp02, heart rate	NONIN Onyx II BT
-	Spirometry	Vitalograph Asma-1

- Fasting Glucose

Study participants will receive training provided by USECARE affiliated organizations at baseline data collection to introduce them to the intervention tool (baseline questionnaire filled out before training starts). The training will include reporting methodology and appropriate use of the SENACA hardware delivered in a pre-configured carrying case. One to two days of practicing connection to the national centre and use of hardware will take place after the training session from the private home of the participants. Two attempts to use hardware and deliver data will be performed prior to initiation of the study. Then, study participants will use the website and monitoring devices on a frequent basis. Failure to communicate or use the hardware will be supported and fixed by the national team. An inability of participants to perform training tasks will be recorded and analysed using standard technology acceptance measurements and qualitative methods (phone interviews).

The study participants will be instructed to use the enhanced SENACA prototype at home up to 3-months (100 days). They will visit local healthcare providers three times for standard clinical procedures (i. e. laboratory tests). Suggested care plans will be provided and shared with end-users (and summary of visit reports are to be provided by the nurse to the participant to share with her or his doctor if needed).

All study participants – if finished the self-management program as prescribed for a duration of six months and continuing to actively use the system – will be offered the complete system for free including a further half-year of service cost.

#### 2.2.4 Theoretical framework for usability study

The Part I preliminary studies within USECARE AAL are guided by an often used framework to understanding older adults' usage and non-usage of modern technology, the technology acceptance model (TAM), which is considered to be valid and robust (Davis, 1989; King & He, 2006; Holden & Karsh, 2010). In its original version, the intention to use technology (often described as technology acceptance) is determined by two key constructs: perceived usefulness (PU), defined as the extent to which people believe that technology will help them perform their task and perceived ease of use (PEOU) which indicates the degree to which a person believes that using a particular system would be free of effort (Davis, 1989; Straub, Keil & Brenner, 1997). A system high in perceived usefulness is one for which a user believes in the existence of positive use-performance relationship, making perceived usefulness the most important predictor of technology acceptance. The TAM has been widely field-tested and enhanced by several researchers, e.g. to further concentrate on influencing context factors (Venkatesh, 2000) or to assign the key determinants in a temporal order (Peek et al., 2014). Further analyses show that the key constructs PU and PEOU can be predicted by personality traits of potential users so that those with high levels of optimism and innovativeness and low levels of insecurity and discomfort have a higher probability to perceive technology as useful and as easy to use (Walczuch et al., 2007). The determinants of the original TAM will be tailored to the setting of USECARE AAL.

Following the TAM's key constructs, *usability* for this study can be defined the ease with which a system can be learned and used (De Vito Dabbs et al., 2009; Preece et al., 1994). This includes, amongst others, *learnability* (ease with which a device can be learned), *effectiveness* (perceived usefulness for supporting intended tasks), *efficiency* (perceived ease with which the device can be used), *errors* (low frequency, severity of errors and easy recovery), and *user satisfaction* (pleasance of use) (see annex 2a). Other constructs like *memorability* (ease with which users can return to the system without relearn) and *flexibility* (variety of ways to achieve intended tasks) will not be addressed due to the research design.

#### 2.2.5 Variables and Measurements

To evaluate the usability (Part I) and evolution of various parameters hypothesized to be responsive to the enhanced SENACA prototype (Part II), the following variables will be addressed and measured with measurements listed in table 3 (additional information on parameters and questionnaires is also listed in the annex section):

Parameters	Mode	Variable	Description	Definition
	Self-reported	Age		Year of birth
		Sex		Sex of participants
Socio-demographics		Education		Number of years in education and highest degree
		Work status		Work status
		Marital status		Legal status
		Cohabitation		Living arrangement
		Nationality		Nationality of respondent & Language skills
		Caregiver relation		Person who is considered as the most important caregiver

#### Table 3. Overview variables and measurements

#### Table 4. Aims Part Ia: preliminary study (usability)

	Self-reported	Perceived Ease of Use		Efficiency
		Perceived Usefulness		Effectiveness
lity		Intention to Use (subjective)		Planned behaviour of technology acceptance
Usabi		Acceptance (subjective)	Process parameters	Uptake, adherence, frequency, variety and intensity of use
		Refusal (subjective)		Reasons for not accepting the product
		Errors		Number and type of problems reported

		User satisfaction	PSSUQ		
	Automatically	Relative frequency of usage of SENACA's modules		Record of the usage of single components that are not mandatory	
	Adherence to SENACA prototype			Number of days within program from initiation to discontinuation (time to event)	
		Errors of SENACA system during implementation		Number and type of technical problems occurring	
Literacy & Readiness	Self-reported	Optimism/ Innovativeness/ Insecurity/ Discomfort	Factors that measure personal traits	item battery of TRI	
eHealth I Technology F		eHealth Literacy	Factors that measure health literacy related to use of electronic devices	eHEALS	

Table 5. Aims Part II: pre-experimental design	(outcome parameters SENACA effects)
--	-------------------------------------

	Automatically	Body Fat	fat proportion of body (%)	
		Weight	Body weight in kg	
		Blood Pressure	Systolic / diastolic mmHg	
		Pulse	per minute	
		SpO2 (only where needed)	in %	
_		Fasting glucose	mmol	
Clinica		One-second forced exhalation, FEV1	%	
	Laboratory	Cholesterol, LDL	mmol	
		Cholesterol, HDL	mmol	
		Total cholesterol	mmol	
		Triglyceride	mmol	
		HbA1c	mmol	
		BNP	pg/ml	
	Self-reported	Height	Centimetres	

Self-efficacy, health-related QoL & burden of care	Self-reported	Quality of Life Health status Self-efficacy	Factors that measure the overall life quality	EQ5D5L: 5 Dimensions Mobility, Self-Care, Usual Activities, Pain/Discomfort, Anxiety/Depression Question to measure overall health status Self-efficacy for managing chronic disease scale (SES6) (question from IL,
		Burden of care		[name])
	Self-reported	Nutrition & Alcohol consumption		Weekly unit consumption
Behavioural		Physical activity		Exercise and walking
		Smoking		Smoking behaviour
	Automatically	Physical activity		Personal logbook/ pedometer

#### 2.2.6 Data collection

The data collection for this study is intended to collect sufficient and appropriate data to identify usability-related issues and to observe parameters on health-related behaviour and clinical outcomes. Once ethics approval is granted, the primary investigator (PI) and the coordinator of USECARE will liaise with the co-investigators in the participating countries and their collaborating clinical settings. When informed consent of eligible participants is obtained, empirical data will be collected by the prototype's measurements (automatically and self-reported), laboratory tests of blood samples, self-reported written questionnaires and using qualitative research methods (interviews).

#### Measurements

Time points of measurements before, during and after the implementation of the prototype are listed in table 6:

		Time points						
Parameters	Variable	automatically	(bi-)/ weekly	Day 0	Day 50	Day 100		
	Age			Х				
S	Sex			Х				
raphi	Education			X				
Bom	Work status			х				
io-de	Marital status			X				
Soc	Cohabitation			x				
	Nationality			x				
	Body Fat	Х		Х				
inical	Blood Pressure	x		x				
Ū	Pulse	x		х				
	SpO2	x		х				
	Fasting glucose	x		x				
	One-second forced exhalation, FEV1	x						
	Cholesterol, LDL			х	x	x		
	Cholesterol, HDL			x	x	x		
	Total cholesterol			х	х	x		
	Triglyceride			Х	Х	x		
	HbA1c			X	X	x		
	Weight			х	X	x		
	Height			х				

#### Table 6. Overview time points of measurements

	Disease history			X		
ad	Quality of Life (EQ5D-5L)		(X)	х	Х	Х
acy a ated (	health status		(X)	X	X	x
Self-effic Health-rel	Self-efficacy for managing chronic disease			x	x	x
ral	Nutrition & Alcohol		(X)	X	x	x
aviou	Smoking			х	X	x
Beh	Physical activity	х		X	x	x
	Perceived Ease of Use (Efficiency)			X	x	x
	Perceived Usefulness (Effectivenes s)			x	x	x
	Intention to Use (subjective)			x	x	x
ability	Acceptance (objective)			x	x	x
SU	Prototype- adherence	x			x	x
	User satisfaction				x	x
	Relative frequency of usage of SENACA's modules	x			x	x
	Errors	х			X	x
th Literacy & ogy Readiness	Individual personal traits predicting technology acceptance			x		
eHea Techno	eHEALS (8 items)			x	x	x

#### Interviews

To gain a deeper understanding of the end-user's experience with the SENACA prototype, a series of semi-structured interviews (Creswell, 2007) with the study participants will be carried

out in the respective languages of the countries involved. Those community-dwelling older adults and informal caregivers finishing the SENACA program will be invited to participate in an interview as will be the ones who potentially discontinue before completing the program. The invitation starts two or three days after completion or drop-out and interviews will be conducted by phone. The intention of reaching data saturation will guide the recruitment procedure and number of participants invited.

By applying a semi-structured interview guide and using open-ended questions, the study participants will be encouraged to elaborate and to describe their experiences with the SENACA prototype in detail (see annex 6). Participant answers will be recorded digitally, transcribed verbatim and translated into English for later analysis.

#### 2.2.7 Ethical considerations

Ethical approval will be obtained in the participating countries before recruiting participants for the study. The participants will receive written information about the study objectives and procedures (see annex 8). They will also be informed about possible risks and benefits including the further use of the system for 12 months at no cost. They will be advised about their right to discontinue their participation at any time. Written informed consent will be obtained.

A high security server will be used for data security of personal information of participants, which will be encrypted for transmission via the data aggregator installed in their households. Throughout the study, investigators will have access to the participants' personal health record using their consent log-in and password (same procedure holds for the treating resident physician / healthcare provider and the informal caregiver, identified on the basis of the SuisseID solution).

#### 2.2.8 Data analysis

Explorative and descriptive data analyses will mainly be performed in this field-test study with a relatively small sample size.

First, descriptive analysis on usability will give a general overview of how users, both informal carers and patients, view SENACA before having used it. The findings will be compared with perceived usability after having experienced it for the whole intervention period (up to day 100). This will provide insights on practical implications on the design and introduction of SENACA. A qualitative analysis on break-offs and non-response further completes the findings by exploring the barriers and drivers of usage. In addition to that, the usage of the several components of SENACA will be compared regarding frequency and intensity to explore which aspects are more or less accepted by the user groups.

In a second step, the clinical and behavioural parameters and quality of life will be screened at baseline measurement. This initial description gives further insights into the characteristics of the sample. Changes in parameters over time will be explored to gain insight into the functionality of SENACA.

Overall, mean values will be compared on the basis of non-parametric tests to identify significant differences between groups. Even though the study does not meet the requirements of an experimental design, the ex-ante and ex post measurement allows monitoring changes of the observed variables. Bias due to non-observable errors may be possible.

Data from qualitative study parts (i.e. interview transcripts, content from open-ended questions or user forums) will be coded applying thematic analysis (Bradley, Curry & Devers, 2007) in order to categorize the data as well as to identify patterns leading to a nuanced evaluation of the usability of SENACA from a technological, educational and behaviour perspective. The qualitative analysis will be guided by taxonomies and frameworks on the subject of matter to be used as sensitizing concepts, for instance Michie et al. (2013) or Greenhalgh et al.(2015). Computer-aided qualitative data analysis (most likely MaxQDA®) will be used for coding and synthesising the findings.

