# 6 Annexes

#### 6.1 Annex 1 – Additional information on measurements

#### Part I – preliminary studies: usability

Usability of the enhanced SENACA prototype will be evaluated during the implementation in view of user's expected perceived usability and user's experienced perceived usability (see Figure 3). Both will be assessed using the three subscales of the TAM measuring perceived usefulness (PU), perceived ease of use (PEOU) and intention to use at the three time points  $(T_1-T_3)$  (see annex 2a). Furthermore the items of the PSSUQ will be applied (see annex 2b). The TAM is considered a valid and robust model (45). In sum, it consists of a 9-item instrument evaluating four statements on the main determinants of intention to use (PU and PEOU) and one on the planned behaviour respectively the intention to use (IU). While statements on perceived ease of use refer more to the aspect of effortlessness in using ICT applications, statements on perceived usefulness refer rather to perceived benefits gained by the use of technology (see theoretical notes in background section). All subscales are rated on a 7-point Likert-scale (1 = 'extremely unlikely' to 7 = 'extremely likely') (see annex 2a). The TAM measures are brief and easy to use and have good reliability (Cronbach's alpha ranging from 0.82 to 0.98) and good convergent validity (> 0.6) (44,52). The wording of the items will slightly be modified in order to fit the setting of USECARE AAL. Two separate versions will be developed to apply to the pre- and post-implementation periods. In addition, items from Technology Readiness Index will be included to predict technology acceptance or rather perceived ease of use and perceived usefulness on the individual level (25,53,54) (see annex 2c).

The usability parameters will also include the percentage of approached potential users not willing to participate, the attrition rate (number of participants discontinuing with the program during the intervention period), the participants' performance (e.g. completion of self-management tasks) and the percentage of days / households without malfunctioning of the system (devices and website) (see annex 6).

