# Part II – pre-experimental design: Quality of life (QoL), health-related behaviour and clinical parameters

A main study parameter is **QoL**, which will be assessed using the EQ-5D (the EuroQol 5dimension inventory) as a generic standardised measure of health status with low respondent burden that provides a cognitively simple, generic measure of health for clinical and economic appraisal (55). The EQ-5D system consists of a self-classifier descriptive system with five dimensions (mobility, self-care, usual activities, pain / discomfort, and anxiety / depression), with each dimension described at five response levels, roughly corresponding to having no, slight, moderate, severe, and extreme problems. The EQ-5D-5L also includes a vertical visual analogue scale (VAS) to enable respondents to provide a self-rating of his or her own health (endpoints with "0" labelled "worst imaginable health" and "100" labelled "best imaginable health"). Although the EQ-5D-5L has been primarily designed as pen-and-paper self-complete instrument, it is available in alternative formats and modes of administration, i.e. for tablet, web or telephone. The EQ-5D-5L and the EQ-5D VAS will be administered at baseline, after 50 days, and along with the final clinical assessment through the web-site interface. Participants will have the option to use the EQ-5D-5L biweekly for voluntary self-monitoring of their quality of life.

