## Only for drop-outs:

10: Could you tell us the main reasons why you decided to stop participating in the study?

0.

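### No TAM, PSSUQ or EQ-5D-5L score is sought when a participant stops using SENACA, so the scored before/after comparison may be biased by selective drop-out

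*Protocol*

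**What the plan says.** **Comparison.** Section 2.2.8 starts with a descriptive overview of how both user groups see SENACA before using it. It continues: "The findings will be compared with perceived usability after having experienced it for the whole intervention period (up to day 100"). For those who stop or do not respond it adds: "A qualitative analysis on break-offs and non-response further completes the findings by exploring the barriers and drivers of usage".

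**Schedule.** Annex 1 has the TAM measure "perceived usefulness (PU), perceived ease of use (PEOU) and intention to use at the three time points". Table 6 places these at Days 0, 50 and 100 and user satisfaction (the PSSUQ) at Days 50 and 100. Annex 1 has the EQ-5D-5L and its visual analogue scale (VAS) "administered at baseline, after 50 days, and along with the final clinical assessment through the web-site interface".

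**People who stop.** Section 2.2.6 says that participants who finish "will be invited to participate in an interview as will be the ones who potentially discontinue before completing the program". It adds: "The invitation starts two or three days after completion or drop-out and interviews will be conducted by phone". The number invited is guided by data saturation. Annex 6 is a structured form on starting, pausing and using SENACA. Its last item, for drop-outs only, asks: "Could you tell us the main reasons why you decided to stop participating in the study". Table 4 lists days from initiation to discontinuation, and Annex 1 lists the attrition rate among the usability parameters.

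**Limitations.** Section 2.2.9 names the missing control group and missing randomisation as sources of bias. It does not name attrition.

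**The concern.** Usability is objective Ia, and section 2.3 expects the results to show which features to optimise before scaling up. The protocol's own background (2.1) says that poorly aligned eHealth tools risk being abandoned. Section 2.2.4 calls perceived usefulness the most important predictor of acceptance. On that reasoning, stopping is related to the score being measured.

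If the Day 0 description covers everyone and the later score covers those still answering, two things are mixed. The people scored later may not represent all who started. The before and after means may also rest on different people, so their difference is not purely a change within persons.

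The attrition rate and time to discontinuation show how many left and when, but not how leavers rated the system. The choice of analysis set can be left to an analysis plan. Whether a score is collected at discontinuation cannot, because no later plan can recover a questionnaire that was never given.

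**Working it through.** The protocol states no sample size, drop-out rate or expected score, so there is no figure to reproduce. The check has two parts.

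**1. Which scores each type of participant would have, followed as written**
- Reaches Day 100: TAM at Days 0, 50 and 100; PSSUQ at Days 50 and 100; EQ-5D-5L at all three (Table 6).
- Stops between Day 50 and Day 100: Day 0 and Day 50 scores. Nothing is specified at stopping beyond Annex 6 and a possible interview. Section 2.2.8 does not say that the Day 50 score enters the comparison.
- Stops before Day 50: Day 0 scores, with no post-use score provided for at stopping. The protocol does not say whether the Day 50 and Day 100 questionnaires are still sought.
- Cannot perform the training tasks: section 2.2.3 applies technology acceptance measurements and phone interviews.

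**2. What missing scores do to the result**

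Let d be the share of starters without a post-use score, C the mean of those scored and D the mean that the unscored would have given.
- All-starter mean = (1 − d) × C + d × D.
- Overstatement of the post-use mean = C − [(1 − d) × C + d × D] = d × (C − D).

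Now let b_C and b_D be the Day 0 means of the same two groups. If Day 0 covers everyone and the later mean covers only those scored:
- Apparent change = C − [(1 − d) × b_C + d × b_D] = (C − b_C) + d × (b_C − b_D).

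The second term comes only from comparing different people. It disappears if change is computed in the same persons. The d × (C − D) term does not disappear, and only scores from leavers can reduce it.

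*TAM item.* Seven response levels give a range of 6. Values of d and of the gap C − D are assumed:

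| d | gap 0 | gap 0.5 | gap 1 | gap 2 |
|---|---|---|---|---|
| 10% | 0 | 0.05 | 0.1 | 0.2 |
| 20% | 0 | 0.1 | 0.2 | 0.4 |
| 40% | 0 | 0.2 | 0.4 | 0.8 |

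The largest value is 0.8 / 6 = 13% of the range.

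*EQ VAS (0 to 100).* With the same d, assumed gaps of 5 to 20 points give 0.1 × 5 = 0.5 to 0.4 × 20 = 8 points. A gap of −10 gives −1 to −4 points, an understatement.

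*Worst-case bounds.* With no score from leavers, the all-starter mean is known only to within d × range. At d = 20% this is 0.2 × 6 = 1.2 TAM points or 0.2 × 100 = 20 VAS points.

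**The case against.** The strongest reply is that the protocol is silent here and does not state an exclusion. Four stronger readings are tempting, and the document does not support them.
- *The comparison is limited to 100-day completers.* Section 2.2.8 says up to Day 100 and names no completer set. The design is a one-group pre-test/post-test with repeated measures, and nothing says that the comparison is unpaired. Day 50 scores are scheduled.
- *Those who gave up are missing from the study.* They have Annex 6, interviews with their own guide in Annex 10, the attrition rate and time to discontinuation. A product that drives people away would show a higher attrition rate beside any TAM score.
- *EQ-5D-5L is lost once people stop logging in.* The website clause in Annex 1 may govern only the final assessment. The same annex notes that a telephone format exists, and section 2.2.6 lists written questionnaires. Loss is possible but not established.
- *Usability and quality of life are overstated.* For usability an upward bias is plausible. For quality of life the direction depends on who stops and why.

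The study is also exploratory. It says that hypothesis testing is not possible and describes its analysis as primarily descriptive.

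All of this stands and narrows the point. It does not remove it: no sentence commits to seeking the three scales at discontinuation, the plan for break-offs is qualitative, saturation sampling need not reach every leaver, and attrition is absent from the limitations. A descriptive mean is as open to selective loss as a tested one.

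**Conclusion.** The point holds in a limited form. As worded, the scored before/after comparison may be biased by selective drop-out, because scores at discontinuation are not provided for. The bias is probably upward for usability, on the assumption that poor fit is a reason to stop, which the protocol's own background supports. For quality of life the direction is unknown.

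The size cannot be determined from the document. The 0.05 to 0.8 TAM points rest wholly on an assumed 10% to 40% unscored and an assumed gap of 0.5 to 2 points, and the bias is zero if there is no gap. Day 50 scores, if used, would reduce the share unscored. This is a cheap improvement to an exploratory study and does not invalidate its design.

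**What to change.** - **2.2.6 and 2.2.8, collection:** state that TAM, PSSUQ and EQ-5D-5L are sought from every starter at discontinuation, with the planned drop-out contact or the Annex 6 form. Seek them also at Days 50 and 100, by paper or phone for anyone who no longer logs in.
- **2.2.8, analysis:** compute before/after change in the same persons. Show Day 0 and any Day 50 scores of completers beside those of discontinuers, together with the attrition rate.
- **2.2.8, summary:** present an all-starters summary using the last available post-use score alongside the Day 100 summary. It should not replace the Day 100 summary, because it mixes lengths of exposure.
- **2.2.9:** name attrition as a possible source of bias.

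The cost is a somewhat longer existing contact: 9 TAM and 18 PSSUQ items, so 9 + 18 = 27, plus the EQ-5D-5L. All drop-outs must be contacted, beyond those needed for data saturation. Some will still decline, so the bias is reduced but not eliminated.
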